## **2 ETHICAL CONSIDERATIONS**

### **2.1 Good Clinical Practice**

This study will be conducted in accordance with Good Clinical Practice (GCP), as defined by the International Conference on Harmonisation (ICH) and in accordance with the ethical principles underlying European Union Directive 2001/20/EC and the United States Code of Federal Regulations, Title 21, Part 50 (21CFR50).

The study will be conducted in compliance with the protocol. The protocol and any amendments and the participant informed consent will receive Institutional Review Board/Independent Ethics Committee (IRB/IEC) approval/favorable opinion prior to initiation of the study.

All potential serious breaches must be reported to Bristol-Myers Squibb (BMS) immediately. A serious breach is a breach of the conditions and principles of GCP in connection with the study or the protocol, which is likely to affect, to a significant degree, the safety or physical or mental integrity of the participants of the study or the scientific value of the study.

Personnel involved in conducting this study will be qualified by education, training, and experience to perform their respective tasks.

This study will not use the services of study personnel where sanctions have been invoked or where there has been scientific misconduct or fraud (eg, loss of medical licensure, debarment).

### **2.2 Institutional Review Board/Independent Ethics Committee**

Before study initiation, the investigator must have written and dated approval/favorable opinion from the IRB/IEC for the protocol, consent form, participant recruitment materials (eg, advertisements), and any other written information to be provided to participants. The investigator or BMS should also provide the IRB/IEC with a copy of the IB or product labeling information to be provided to participants and any updates.

The investigator or BMS should provide the IRB/IEC with reports, updates and other information (eg, expedited safety reports, amendments, and administrative letters) according to regulatory requirements or institution procedures.

### **2.3 Informed Consent**

Investigators must ensure that participants are clearly and fully informed about the purpose, potential risks, and other critical issues regarding clinical studies in which they volunteer to participate.

In situations where consent cannot be given to participants, their legally acceptable representatives (as per country guidelines) are clearly and fully informed about the purpose, potential risks, and other critical issues regarding clinical studies in which the participant volunteers to participate.

BMS will provide the investigator with an appropriate (ie, Global or Local) sample informed consent form(s) which will include all elements required by ICH, GCP, and applicable regulatory requirements. The sample informed consent form will adhere to the ethical principles that have their origin in the Declaration of Helsinki.

Investigators must:

- Provide a copy of the consent form(s) and written information about the study in the language in which the participant is most proficient prior to clinical study participation. The language must be non-technical and easily understood.
- Allow time necessary for participant or participant's legally acceptable representative to inquire about the details of the study.
- Obtain an informed consent signed and personally dated by the participant or the participant's legally acceptable representative and by the person who conducted the informed consent discussion.
- Obtain the IRB/IEC's written approval/favorable opinion of the written informed consent form(s) and any other information to be provided to the participants, prior to the beginning of the study, and after any revisions are completed for new information.
- If informed consent is initially given by a participant's legally acceptable representative or legal guardian, and the participant subsequently becomes capable of making and communicating his or her informed consent during the study, consent must additionally be obtained from the participant.
- Revise the informed consent whenever important new information becomes available that is relevant to the participant's consent. The investigator, or a person designated by the investigator, should fully inform the participant or the participant's legally acceptable representative or legal guardian, of all pertinent aspects of the study and of any new information relevant to the participant's willingness to continue participation in the study. This communication should be documented.

The confidentiality of records that could identify participants must be protected, respecting the privacy and confidentiality rules applicable to regulatory requirements, the participants' signed ICF.

The consent form(s) must also include a statement that BMS and regulatory authorities have direct access to participant records.

Participants unable to give their written consent (eg, stroke or participants with or severe dementia) may only be enrolled in the study with the consent of a legally acceptable representative. The participant must also be informed about the nature of the study to the extent compatible with his or her understanding, and should this participant become capable, he or she should personally sign and date the consent form as soon as possible. The explicit wish of a participant who is unable to give his or her written consent, but who is capable of forming an opinion and assessing information to refuse participation in, or to be withdrawn from, the clinical study at any time should be considered by the investigator.

The rights, safety, and well-being of the study participants are the most important considerations and should prevail over interests of science and society.

### 3 INVESTIGATIONAL PLAN

#### 3.1 Study Design and Duration

##### 3.1.1 Overall Design and Schematic

This is an open-label, multi-dose, 2-part, Phase 1/2 study of nivolumab in combination with ipilimumab in Chinese participants with previously treated metastatic or recurrent solid tumors.

As of 20-Dec-2021, the study was closed to new enrollment for Part 2, and a total of 36 participants (9 participants each in Arms A, B, C, and D) were treated in the 3 nivolumab/ipilimumab combination dosing regimens as described below and in Table 3.1.1-1. For all arms, treatment was not randomized.

In Part 1, 9 participants were treated in each of the three arms:

- **Arm A:** Nivolumab administered IV over 30 minutes at 3 mg/kg every 2 weeks combined with ipilimumab administered IV over 30 minutes at 1 mg/kg every 6 weeks
- **Arm B:** Nivolumab administered IV over 30 minutes at 3 mg/kg combined with ipilimumab administered IV over 30 minutes at 1 mg/kg every 3 weeks for 4 doses followed by nivolumab administered IV over 30 minutes at 240 mg every 2 weeks
- **Arm C:** Nivolumab administered IV over 30 minutes at 1 mg/kg combined with ipilimumab administered IV over 30 minutes at 3 mg/kg every 3 weeks for 4 doses followed by nivolumab administered IV over 30 minutes at 240 mg every 2 weeks

In Part 2, a total of 9 participants with recurrent or metastatic MSI-H/dMMR CRC determined by local testing were treated in the following treatment arm:

- **Arm D:** Nivolumab administered IV over 30 minutes at 3 mg/kg combined with ipilimumab administered IV over 30 minutes at 1 mg/kg every 3 weeks for four doses followed by nivolumab administered IV over 30 minutes at 240 mg every 2 weeks.

**Table 3.1.1-1: Nivolumab and Ipilimumab Dose Levels**

Dosing Arm	Nivolumab (mg/kg, frequency)	Ipilimumab (mg/kg, frequency)
A	3 mg/kg, Q2W	1 mg/kg, Q6W
B	3 mg/kg, Q3W × 4 240 mg, Q2W thereafter	1 mg/kg, Q3W × 4
C	1 mg/kg, Q3W × 4 240 mg, Q2W thereafter	3 mg/kg, Q3W × 4
D	3 mg/kg, Q3W × 4 240 mg, Q2W thereafter	1 mg/kg, Q3W × 4

Abbreviations: AEs = adverse events; Ipi = ipilimumab; Q2W = every 2 weeks; Q3W = every 3 weeks; Q6W = every 6 weeks.

Treatment continues until progression, unacceptable toxicity, withdrawal of consent, completion of **maximum treatment duration**, the study ends, or other reasons specified in the protocol, whichever occurs first. Treatment beyond initial Investigator-assessed Response Evaluation Criteria in Solid Tumors (RECIST) 1.1-defined progression is permitted if the participant has investigator assessed clinical benefit and is tolerating nivolumab, as specified in [Section 4.5.7](#).

**Maximum treatment duration** will be 24 months from the first dose of study treatment EXCEPT in participants with late response (during second year of treatment) who may receive for up to an additional 12 months after onset of response, in absence of disease progression, unacceptable toxicity and withdrawal of consent. Above defined maximum treatment duration includes treatment beyond progression.

The study will consist of 3 periods: screening period; treatment period (until disease progression, intolerable toxicities, withdrawal of consent, completion of maximum treatment duration, the study ends, or other reasons specified in the protocol, whichever occurs first); and a follow-up period (up to 100 days for Arms A, B, C, and D). For Part 1, tumor assessment must be completed every 6 weeks for the first 24 weeks from date of first dosing, and then every 12 weeks thereafter until disease progression (including treatment beyond progression) or unacceptable toxicities. For Part 2, tumor assessment must be completed every 6 weeks from date of first dosing for the first 24 weeks, and then every 12 weeks thereafter (including treatment beyond progression) until initiation of subsequent anticancer treatment. See [Section 5.4](#) for details of imaging assessment requirement.

Every effort should be made to schedule visits within the timeframe stated in the protocol.

[figure not shown]
Participants will undergo screening evaluations to determine eligibility prior to administration of study drug. For Part 1 only, for the purpose of PK sample collection, participants will be admitted to the clinical facility prior to dosing (Day -1) only on Cycle 1/Day 1 and Cycle 3/Day 1 for Arm A, and Cycle 1/Day 1 and Cycle 2/Day 22 for Arms B and C, and will remain in the clinical facility until 24 hours after study drug administration.

For Part 2 only, images will be submitted to a central imaging vendor for BICR during the study. Prior to scanning first participant sites should be qualified and understand the image acquisition guidelines and submission process as outlined in the CA209-672 Imaging Manual provided by the central imaging vendor.

[figure not shown]
The study design schematic is presented in Figure 3.1.1-1.

**Figure 3.1.1-1: Study Design Schematic**

Part 1

Part 2

\* If a participant with following tumor types is enrolled, he/she can only be treated using one specific dosing schedule, eg, NSCLC, SCCHN, or mesothelioma participant is to be treated in Arm A only. SCLC participant is to be treated in Arm C only.

\*\*Participants may be treated beyond progression under protocol-defined circumstances. Treatment continues until progression, unacceptable toxicity, withdrawal of consent, completion of maximum treatment duration of 2 years EXCEPT in participants with late response (during second year of treatment) who may receive treatment for up to an additional 12 months after onset of response, the study ends, or other reasons specified in the protocol, whichever occurs first.

**3.1.2 Part 1 - Safety Monitoring**

Physical examinations, vital sign measurements, 12-lead electrocardiograms (ECG), and clinical laboratory evaluations will be performed at selected times throughout the dosing interval. Participants will be closely monitored for adverse events throughout the study. Blood samples will be collected before and after study drug administration for PK analysis.

Less than 350 mL of blood will be drawn from each participant during the study.

In part 1, safety evaluation is planned after a total of 9 participants completed the first 6 weeks of treatment and associated evaluation in a given arm. However, tolerability beyond 6 weeks may

also be taken into consideration. Participants who do not complete the DLT observation period for reasons other than DLTs will be replaced.

The participants' safety will be monitored on an ongoing basis. Adverse events will be reviewed expeditiously by medical monitor and discussed with the study investigators. The sponsor and the study investigators will make an assessment on the tolerability of each combination regimen. Existing clinical safety database from earlier studies may be referred to. The criteria for tolerability Table 3.1.2-1 are based on dose limiting toxicities (listed in [Section 4.5.1](#)) and include:

- If no more than two out of the nine participants in a given treatment arm permanently discontinue study medication prior to Week 6 due to treatment related adverse events, then this dose arm will be deemed as tolerable.
- If at least three out of the nine participants in a treatment arm permanently discontinue study medication prior to Week 6 due to treatment-related AEs, then the safety, tolerability, and efficacy of that treatment arm will be reviewed and discussed by the sponsor and investigators for benefit/risk ratio.

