#### Study Assessments:

- Safety Outcome Measures: Safety assessments will be based on medical review of adverse event reports and the results of vital sign measurements, ECOG status, ECGs, physical examinations, and clinical laboratory tests. The incidence of observed adverse events will be tabulated and reviewed for potential significance and clinical importance. Toxicity will be evaluated by the National Cancer Institute Common Terminology Criteria for Adverse Events (NCI CTCAE) version 4.0.
- Dose-Limiting Toxicity: DLTs are defined in protocol [Section 4.5.1](#) and will be determined based on the incidence, intensity, and duration of adverse event (AE) that are related to study drug, and that occur within 42 days (6 weeks, through completion of cycle 1) of initiation of study drug;
- Not applicable per Protocol Amendment 07: Pharmacokinetic Evaluation: Serial blood samples for pharmacokinetic assessments will be collected from all participants at specified time points.
- Not applicable per Protocol Amendment 07: Immunogenicity Evaluations: Blood samples to evaluate development of positive anti-drug antibody (ADA) response will be collected at specified time points for all participants.

- Efficacy Assessment: Computed tomography/magnetic resonance imaging (CT/MRI) for chest, abdomen, pelvis, and brain will be performed at screening and at specified time points in [Table 5.1-2](#), [Table 5.1-3](#), and [5.1-4](#). Measurement of tumor burden must be reviewed and documented before initiating further treatment with nivolumab. Tumor response status will be assessed with RECIST 1.1.

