**Table 3.1.2-1: Guidance for Safety Monitoring Based on Observed Toxicity Outcomes**

Number of participants treated and followed up for at least 6 weeks after start of study treatment	Number of participants with DLTs	Next Step
9	≤ 2	Tolerable
9	≥ 3	To be discussed between sponsor and investigators to review benefit/risk ratio

The duration of the study is anticipated to be approximately 2 years. The end of the trial will occur on the day of the last visit of the last participant.

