#### **4.5 Selection and Timing of Dose for Each Participant**

##### **4.5.1 Dose Limiting Toxicities**

Dose limiting toxicities are defined as any of the items listed below which occur during the first 6 weeks.

- Any Grade 2 drug-related uveitis or eye pain that does not respond to topical therapy and does not improve to Grade 1 severity within the re-treatment period OR requires systemic treatment
- Any Grade 2 drug-related pneumonitis or interstitial lung disease that does not resolve to dose delay and systemic steroids.
- Any Grade 3 non-skin drug-related adverse event regardless of duration with the exception of laboratory abnormalities
- Any Grade 4 drug-related adverse event including laboratory abnormalities except Grade 4 leukopenia or neutropenia lasting < 7 days
- Any of the following drug-related hepatic function laboratory abnormalities:
  - Grade  $\geq$  3 drug-related AST, ALT or Total bilirubin
  - Concurrent AST or ALT  $>$  3 x ULN and total bilirubin  $>$  2x ULN
  - Grade 3 thrombocytopenia associated with bleeding

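### Section 3.1.2 says Part 1 tolerability rests on DLTs, but its two bullets apply the same cut-off (2 or fewer versus 3 or more of 9) to permanent discontinuations, so text and table can classify one arm differently

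*Combined protocol and SAP*

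**What the plan says.** Section 3.1.2 introduces the Part 1 rule with the sentence "The criteria for tolerability Table 3.1.2-1 are based on dose limiting toxicities" and points to the list in Section 4.5.1. Two bullets then state the criteria. The first begins "If no more than two out of the nine participants in a given treatment arm permanently discontinue study medication prior to Week 6" and, where the reason is a treatment-related adverse event, calls the arm tolerable. The second sends an arm with three or more such discontinuations to a benefit/risk review by the sponsor and investigators.

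Table 3.1.2-1, directly below, puts the same cut-off on a different column, "Number of participants with DLTs". The Synopsis repeats that table. The replacement rule is also in DLT terms: "Participants who do not complete the DLT observation period for reasons other than DLTs will be replaced". Section 8.1.1 justifies nine participants per arm by exact upper bounds on the DLT rate. The Synopsis (Study Assessments) sets the DLT window as events "that occur within 42 days (6 weeks, through completion of cycle 1) of initiation of study drug".

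**The concern.** One section holds two decision rules with identical thresholds and different counted events. If DLTs and early discontinuations were the same event, this would be loose wording. They are not, so the same data can give two answers: the bullets call the arm tolerable while the table refers it for discussion. DLTs are named in the Part 1 primary objective (Section 1.3.1), so the reader of the study report needs to know which count stands behind the word tolerable.

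**Working it through.** **1. The plan's own figure.** Section 8.1.1 gives upper limits of 23%, 37%, 49% and 60% for 0, 1, 2 and 3 DLTs in 9. The Clopper-Pearson one-sided 90% upper limit for x of 9 is the 0.90 quantile of Beta(x+1, 9−x). This gives 22.57%, 36.84%, 49.01% and 59.94%. The stated limits are reproduced; the third is 49% only after rounding. The sample-size text is sound, and it concerns DLTs.

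**2. Are the two events the same?** Section 4.5.1 (DLT list) against Section 4.5.6 (discontinuation criteria):

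- *Overlap.* Grade 3 uveitis, pneumonitis, bronchospasm, diarrhea, colitis, myocarditis, neurologic toxicity, hypersensitivity and infusion reactions are DLTs and require discontinuation at any duration. Grade 3 or higher AST, ALT or bilirubin is a DLT and usually leads to discontinuation.
- *DLT, discontinuation not required.* The DLT list includes "Any Grade 3 non-skin drug-related adverse event regardless of duration with the exception of laboratory abnormalities". Section 4.5.6 generally requires discontinuation for such events only beyond 7 days. So a Grade 3 non-skin event of 7 days or less, outside the any-duration list, is a DLT only. So is a Grade 3 endocrinopathy controlled by hormone replacement, other than adrenal insufficiency. So is an isolated Grade 4 amylase or lipase rise without pancreatitis: Section 4.5.6 exempts it, and the Grade 4 item of Section 4.5.1 does not.
- *Discontinuation required, not a DLT.* Grade 3 thrombocytopenia beyond 7 days without bleeding. The DLT item requires bleeding.

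**3. Consequence.** Take an arm with three DLTs, one of them a hormone-controlled Grade 3 endocrinopathy that continues treatment. It has 3 of 9 DLTs and 2 of 9 discontinuations. The table says discuss; the bullet says tolerable.

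**4. How often? Illustration only.** The documents give neither the 6-week DLT rate p nor the share f of participants with a DLT who discontinue early. Both are assumed here. Assume also that nobody discontinues without a DLT, so only one direction of disagreement is counted.

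With D ~ Bin(9, p) DLTs and X given D ~ Bin(D, f) discontinuations, X ~ Bin(9, pf). Because X cannot exceed D,

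P(D ≥ 3 and X ≤ 2) = P(D ≥ 3) − P(X ≥ 3).

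For p = 0.30 and f = 0.75, pf = 0.225 and the result is 0.5372 − 0.3296 = 0.2076.

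| p | P(D ≥ 3) | f = 0.90 | f = 0.75 | f = 0.50 |
|---|---|---|---|---|
| 0.10 | 0.0530 | 0.0125 | 0.0278 | 0.0446 |
| 0.20 | 0.2618 | 0.0513 | 0.1209 | 0.2088 |
| 0.30 | 0.5372 | 0.0819 | 0.2076 | 0.3963 |

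The 30% row lies near the top of the Grade 3-4 treatment-related rates reported for these regimens: 19% and 30% in SCLC (Section 1.1.4), 28% in NSCLC (Table 1.4.4.4-1) and about 32% in colorectal cancer (Section 1.1.1). Those cover the whole of treatment and include skin and laboratory events that are not DLTs, so a 6-week DLT rate may well be lower. They cannot stand in for p.

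**The case against.** The strongest reply is that nothing turns on this now. Section 3.1.1 records that "In Part 1, 9 participants were treated in each of the three arms". Arm D, on the same regimen as Arm B, has since been opened, filled to nine and closed. The table is titled as guidance and its upper branch is a discussion. Section 3.1.2 adds that "The sponsor and the study investigators will make an assessment on the tolerability of each combination regimen", whatever the count, and lets them draw on tolerability beyond six weeks and on earlier studies. The 6-week counts already exist; if both fall on the same side of the cut-off in all three arms, the practical effect is nil. All of this stands, and it limits the point to reporting.

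A reader might infer more from Sections 8.3.1.1 and 8.4.3, which name no DLT count: that the plan drops the DLT result altogether. The documents do not support that. The Synopsis lists DLT as an assessment with its own definition and window, the table cannot be applied without a count per arm, and Section 8.1.1 supplies the interval. A separate statistical analysis plan is cited in Sections 8.3.2.1 and 8.4.8 for immunogenicity details, and its text is not available here. The silence is mostly missing detail.

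It is also fair to object that editing a decision rule after an open-label part has been treated is retrospective, since both criteria are in the current text. That argues for making the correction openly and showing both counts. It does not argue for leaving the contradiction in place.

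**Conclusion.** The inconsistency is real and can be read directly from Section 3.1.2. The bullets are the outlier: the lead-in sentence, both tables, the replacement rule and Section 8.1.1 all use DLTs. Followed literally, the bullets can call an arm tolerable that the table refers for benefit/risk discussion.

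The size cannot be established from the documents. Under the assumed ranges the chance per arm is 1% to 4% at a 10% DLT rate, 5% to 21% at 20%, and 8% to 40% at 30%. These show that the two counts are not interchangeable. They do not estimate what happened in Arms A, B and C.

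A reader might conclude that a dosing or arm decision was compromised, or that nine per arm was wrongly justified. Neither follows: the documents report no DLT or discontinuation counts for Part 1, the upper branch is only a discussion, and the Section 8.1.1 bounds reproduce. The adverse event endpoints of Section 8.3.1.1 do not depend on the rule either. What is at stake is which count supports the reported tolerability conclusion. It should be corrected.

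**What to change.** State in Section 3.1.2 that the DLT count of Table 3.1.2-1 governs (Section 4.5.1 events within 42 days of first dose), correct the two bullets to match, and record in the change summary that the section had held both criteria.

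Add one table to the Part 1 safety output. For each arm it should give:

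- the number and percent of participants with DLTs, with the exact one-sided 90% upper bound of Section 8.1.1;
- beside it, the number who permanently discontinued before Week 6 for treatment-related adverse events;
- a flag on any arm where the two counts fall on different sides of the cut-off.

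The cost is a small wording change and one table from adverse event data already collected. A protocol change has to follow the review steps of Section 9.1.1. If the sponsor does not want to reopen the protocol of a closing study, the same statement and table in the analysis plan and study report would cover the reporting need, though the contradictory text would remain on file.
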